## 2. RATIONALE

We undertook a survey to identify current clinical practice amongst breast cancer centres in the UK. Of the 70 responding hospitals, 79% performed ALND, 9% undertook ART and 12% SNB or axillary node sampling (ANS) [unpublished data]. The survey showed that clinicians are at equipoise and 99% of the respondents expressed willingness to randomise patients in the ATNEC trial.

This research question has been identified as a priority by patients at many different cancer support groups and events, including the Macmillan patient focus group, Independent Cancer Patients' Voice, Dragon's Den at the National Cancer Research Institute's (NCRI) consumer forum, NCRI Breast CSG, UK Breast Intergroup and NCRI Clinical and Translational Radiotherapy Research Working Group (CTRad). The NCRI Living with and Beyond Cancer Initiative highlights that it is important to cancer patients to live better with and beyond cancer. The number one priority concerns looking at the long-term side effects of cancer treatment, confirming the importance of this study to patients [14].

The ATNEC research question has also been identified as a key research gap by Association of Breast Surgery [15]. The UK multidisciplinary guidance published in 2019 advises that patients with no residual disease in the sentinel nodes after NACT should receive ART and recommends that clinicians should participate in the ATNEC study to answer this important research question [16]. Thus we anticipate that the study results will lead to updated NICE and specialty guidelines and will change clinical practice in the future.

## 3. AIMS, OBJECTIVES AND OUTCOME MEASURES/ ENDPOINTS

## 3.1. Objectives

The *primary objectives* are to assess whether, omitting further axillary treatment (either ALND or ART) for patients with early stage breast cancer and axillary nodal metastases on needle biopsy, who after NACT have no evidence of residual cancer in the lymph nodes on SNB, is non-inferior to axillary treatment in terms of disease free survival (DFS), and reduces the risk of lymphoedema at five years.

Secondary objectives are:

- I. To compare arm morbidity and quality of life between and within the two allocated groups over five years.
- II. To compare axillary recurrence free interval, breast or chest wall recurrence, regional (nodal) recurrence, distant metastasis, and overall survival, contralateral breast cancer, non-breast malignancy between the two allocated groups over five years.
- III. Economic evaluation

- a. To compare costs to the NHS and to participants over five years
- b. To compare quality-adjusted life years (QALYs) over five years.
- c. To estimate cost-effectiveness measured in terms of incremental cost per disease free interval from the perspective of the NHS and patients over five years
- d. To estimate cost-effectiveness measured in terms of incremental cost per lymphoedema event avoided from the perspective of the NHS and patients over five years
- e. To estimate cost-effectiveness measured in terms of incremental cost per QALY gained from the perspective of the NHS and patients over five years
- f. To extrapolate costs and outcomes over the lifetime of patients with early stage breast cancer and estimate the cost-effectiveness measured in terms of incremental cost per QALY gained from the perspective of the NHS and patients
- IV. Qualitative Evaluation
  - a. To identify and investigate recruitment issues and develop effective and realistic strategies to ensure overall success of the trial

#### 3.2. Outcome

#### 3.2.1. Co-primary outcomes:

- Disease-Free Survival (DFS); defined and calculated as the time from randomisation until the date of first event of either a loco-regional invasive breast cancer relapse, distant relapse, ipsilateral or contralateral new invasive primary breast cancer or death by any cause or the censor date.
- Lymphoedema is self-reported based on two items from the validated Lymphoedema and Breast Cancer Questionnaire (LBCQ) (arm "swelling now" and arm "heaviness in the past year"). These items have been shown to be predictive of arm swelling of a 2 cm or more change in arm circumference, but provide a simpler patient-friendly measure which has been used in other studies [17-19]. Lymphoedema will be defined as 'yes' to both questions at five years.

#### 3.2.2. Secondary outcomes:

- Arm function will be assessed using the shortened version of the Disability of the Arm, Shoulder and Hand (DASH), the 11-item QuickDASH questionnaire [20].
- Pain intensity and characteristics will be measured using questions from the Douleur Neuropathique (DN4) and Pain Numeric Rating Scale (NRS) and will relate to the areas affected by surgery and cancer treatment.
- Axillary recurrence free interval, calculated from the date of randomisation to the date of axillary
  recurrence or the censor date. Axillary recurrence is defined as pathologically (cytology or
  biopsy) and/or radiologically confirmed recurrence in lymph nodes draining the primary tumour
  site, i.e. nodes in the ipsilateral axilla, infraclavicular fossa, supraclavicular fossa and
  interpectoral area. The date of axillary recurrence is the date on which imaging or pathology
  report (whichever comes first) confirms axillary recurrence.
- Overall survival; calculated as the time from randomisation until the date of death by any cause or the censor date.
- Local (breast or chest wall) recurrence is defined as pathologically (cytology or biopsy) and/or
  radiologically confirmed recurrence after mastectomy in the skin or soft tissue of the chest wall
  within the anatomical area bounded by the mid-sternal line, the clavicle, the posterior axillary
  line and the costal margin or any type of breast carcinoma in the breast after conservation

therapy. The date of local recurrence is the date on which the imaging or pathology report (whichever comes first) confirms local recurrence.

- Regional (nodal) recurrence is defined as pathologically (cytology or biopsy) and/or radiologically confirmed recurrent tumour in the lymph nodes in the ipsilateral axilla, infraclavicular, supraclavicular fossa, interpectoral area or ipsilateral internal mammary chain. The date of regional recurrence is the date on which the imaging or pathology report (whichever comes first) confirms local recurrence.
- Distant metastasis is defined as confirmed metastasis (positive pathology and/or definitive evidence on imaging) in all other sites of recurrence and may include those classified as: softtissue category, visceral category, central nervous system and skeletal spread. The date of distant metastasis is the date on which the imaging or pathology report (whichever comes first) confirms metastasis.
- Contralateral breast cancer is defined as a new primary malignancy in the opposite breast unless obviously contiguous with recurrent chest wall disease or proven on cytology/biopsy to be of metastatic origin.
- Non-breast cancer is defined as any new non-breast primary malignancy, except for basal or squamous cell cancer of the skin, in situ carcinoma of the cervix, or in situ or stage 1 melanoma.
- Economic evaluation
  - Costs to the NHS and patients for each randomised group
  - QALYs based on responses to the EQ-5D-5L administered at baseline, 12, 24, 36, 48, and 60 months post-randomisation
  - Incremental cost per disease free interval over five years
  - Incremental cost per lymphoedema avoided over five years
  - o Incremental cost per QALY gained over five years
  - Incremental cost per QALY over the estimated lifetime of a participant with early stage breast cancer

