#### 6.4.8.2 Radiotherapy

Participants in both groups may receive adjuvant breast or chest wall irradiation therapy as per predefined local guidelines. The irradiation therapy for this protocol **specifically excludes** axillary, supraclavicular fossa and internal mammary irradiation when randomised to no further axillary treatment as this would confound the issue being addressed by this study. It is recognised that a variable amount of the axilla may be irradiated unintentionally by standard breast/chest wall tangential fields. However, unless definitive RT to the axilla is selected in preference to axillary node dissection surgery, no attempt should be made to irradiate the axilla by adjustment of the superior/posterior tangential field margins. All participants receiving radiotherapy should be treated according to local guidelines. Participants must also be monitored for compliance according to the ATNEC RT QA planning and delivery guidelines (see Section 9 and accompanying RT QA pack for further details).

In summary:

ALL participants may receive radiotherapy to the breast or chest wall.

Experimental arm (no axillary treatment arm): Radiotherapy to the axilla, supra-clavicular fossa (SCF) and internal mammary chain is **not permitted**.

Control arm (axillary treatment arm, if axillary radiotherapy): participants will receive radiotherapy to the axilla (covering at least level 1 & 2). Participants may receive radiotherapy to SCF and internal mammary chain.

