(axillary	treatment				
treatment)	arm				
11	6	5	691	1382	1846
12	6	6	509	1018	1360
13	6	7	395	790	1054
14	6	8	319	638	852
15	6	9	264	528	704

Additionally, the sample size is sufficient to demonstrate non-inferiority of omitting further axillary treatment in the secondary outcome of axillary recurrence free interval (ARFI) with 90% power and a 5% 1-sided significance level, defining non-inferiority as 'no worse than 2%' below the control arm 5-year ARFI of 98% using the POWER procedure within the SAS statistical software.

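### Regional recurrence is dated by confirmation of local recurrence, and axillary soft-tissue relapse after breast conservation fits none of the loco-regional definitions

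*Protocol*

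**What the plan says.** All the wording at issue is in Protocol Section 3.2.2, unless another section is named.

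- **Axillary recurrence** is nodal. It lists "nodes in the ipsilateral axilla, infraclavicular fossa, supraclavicular fossa and" the interpectoral area. Its date is when a "report (whichever comes first) confirms axillary recurrence".
- **Local recurrence** means the skin or soft tissue of the chest wall after mastectomy, within an area reaching to the posterior axillary line. After conservation it means disease in the breast: "line and the costal margin or any type of breast carcinoma in the breast after conservation" therapy. It is dated by confirmation of local recurrence.
- **Regional recurrence** is nodal: the axillary list plus the ipsilateral internal mammary chain. Its date rule reads: "The date of regional recurrence is the date on which the imaging or pathology report (whichever comes first) confirms local recurrence".
- **Distant metastasis** is the residual class, for confirmed metastasis "in all other sites of recurrence and may include those classified as" soft-tissue, visceral, central nervous system or skeletal. It is dated by confirmation of metastasis.

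Section 3.1 (secondary objective II) compares regional recurrence and ARFI between the arms. DFS in Section 3.2.1 runs to the first event and counts loco-regional and distant relapse alike. Section 10.1 gives ARFI its own power statement, "defining non-inferiority as 'no worse than 2%' below the control arm 5-year ARFI of 98" per cent.

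**The concern.** A date rule is an operative part of a time-to-event endpoint. Here the rule for regional recurrence names an event with its own, different definition. A data manager or programmer who follows it cannot date an isolated nodal relapse, and in a patient with both events will take the breast or chest wall date.

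The second issue is coverage. The trial omits axillary treatment in one arm, so relapse in the axilla is the outcome most directly exposed to that choice. The axillary and regional definitions admit lymph nodes only. A soft-tissue relapse in the same axilla after breast conservation falls outside them, and outside local recurrence as well. If such relapses were more frequent without axillary treatment, leaving them out of ARFI would favour a finding of non-inferiority. The Protocol does not say whether they are.

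**Working it through.** **1. The date rule, case by case.** Let t1 < t2 be the two report dates. The literal result under Section 3.2.2 is:

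| Case | Axillary date | Regional date as written | Regional date evidently meant |
|---|---|---|---|
| Axillary node only, t1 | t1 | none | t1 |
| Internal mammary node only, t1 | not an axillary event | none | t1 |
| Axillary node t1, then local t2 | t1 | t2 (late by t2 − t1) | t1 |
| Local t1, then axillary node t2 | t2 | t1 (early by t2 − t1) | t2 |
| Internal mammary node t1, then local t2 | not an axillary event | t2 (late by t2 − t1) | t1 |

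The regional endpoint is wrong or undefined in every row. For DFS, the axillary and local rules still supply the correct first date in rows 1, 3 and 4. DFS is exposed in rows 2 and 5, where the only nodal disease is in the internal mammary chain. It is also exposed if the database takes its nodal date from the regional field.

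**2. Where an ipsilateral axillary soft-tissue relapse goes.**

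| Definition | After breast conservation | After mastectomy |
|---|---|---|
| Axillary | no: nodes only | no: nodes only |
| Regional | no: nodes only | no: nodes only |
| Local | no: must be in the breast | arguable: the area reaches the posterior axillary line, but the tissue must belong to the chest wall |
| Distant | possible through the residual clause, which names soft tissue | possible if not local |

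After conservation no loco-regional class accepts it. After mastectomy it might be local. The label can therefore depend on breast surgery type.

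**3. Whether any stated figure moves.**

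- *ARFI power.* The inputs are 98% in both arms, a 2-point margin, 5% one-sided significance and 90% power (Section 10.1). n per arm = (1.645 + 1.282)² × 2 × 0.98 × 0.02 / 0.02² = 840, or 1680 in total. With 7% loss (stated for DFS, assumed here for ARFI) this is 1680 / 0.93 = 1807, within 1900. With 950 × 0.93 ≈ 883 per arm, power = Φ(0.02 / √(0.0392 / 883) − 1.645) = Φ(1.357) = 91.3%. The stated 90% is supported on this binary formula.
- *ARFI as time to event.* HR = ln 0.96 / ln 0.98 = 2.02, which needs 70 events. Power is 91.5 to 93.1% if events are counted under 98% v 96%, and 79.5 to 82.0% if both arms are at 98%. That spread comes from how events are projected, not from the site definitions.
- *DFS.* HR = ln 0.865 / ln 0.90 = 1.376. Events = 4 × (1.645 + 1.036)² / (ln 1.376)² = 282, as stated in Section 10.6. A site label does not change whether a DFS event has occurred.

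**4. Scale of the ARFI gap.** At 98%, about 950 × 0.02 = 19 control events are expected at five years, and the margin is another 19. The Protocol gives no count of axillary soft-tissue relapses. If 1, 3 or 5 were left out in one arm (assumed), its estimate would shift by 1/950 = 0.11, 3/950 = 0.32 or 5/950 = 0.53 point. That is 5%, 16% or 26% of the margin.

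**The case against.** The defence has real force on size:

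- The intent of the regional rule is plain. The sentence repeats the wording of the local bullet, and most readers would correct it without being told.
- Every regional site except the internal mammary chain is also in the axillary definition, which is dated correctly. ARFI does not use the faulty sentence at all.
- On soft tissue, the Protocol nowhere sends axillary disease to the distant class. That class requires confirmed metastasis, and soft tissue appears only as an example.
- Type of breast surgery is a minimisation factor (Section 6.3.3), so a difference in labelling by surgery type should be roughly balanced between arms.

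These points limit the consequences but do not remove the error. Regional recurrence is a listed comparison, and its own date rule is wrong as written. This is not detail left to the SAP. The soft-tissue gap also remains: wherever such an event is filed, it is not an ARFI event after conservation.

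A reader might go further and infer that supraclavicular nodes are misfiled under axillary recurrence. One reason would be that Section 6.4.8.2 says of control participants having axillary radiotherapy that "Participants may receive radiotherapy to SCF and internal mammary chain", while the experimental arm may not. The Protocol does not support that inference. The supraclavicular fossa is named expressly as one of the nodal sites draining the tumour, and overlap with regional recurrence is nesting, not contradiction. The radiotherapy difference belongs to the randomised strategies compared by intention to treat. If that irradiation prevents supraclavicular events, counting them makes non-inferiority harder to show, not easier.

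**Conclusion.** The regional date rule is wrong as written. The number of patients affected cannot be worked out, because the Protocol gives no breakdown of recurrence by site or sequence. The error per patient is either a missing date or the interval between the nodal and local reports, in either direction. The damage falls on the regional recurrence comparison. An effect on a DFS date is possible, chiefly for internal mammary recurrence, but not established.

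The soft-tissue point holds as a gap in coverage. It rests on a literal reading of nodes only and in the breast. That such a relapse would be classed as distant is a possible outcome of the residual clause, not a stated rule.

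Two stronger conclusions are not supported. The co-primary DFS result is not put in doubt, since both relapse classes count and the 282 events reproduce. Nor is the ARFI power statement shown to be wrong. The shifts of 0.11 to 0.53 point rest on assumed counts placed in one arm; they show scale and are not a forecast.

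**What to change.** 1. In the regional recurrence bullet of Section 3.2.2, change the final reference from local to regional recurrence, so that the report confirming nodal disease sets the date.
2. State in the same section that soft-tissue recurrence in the ipsilateral axilla counts as axillary, and therefore also regional, recurrence whatever the type of breast surgery. Add that it is not classed as local or distant.
3. Check that the site codes on the Event Form, which is not among the documents seen, and the derivation of the DFS date follow the corrected rules.

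The supraclavicular definition needs no change. The cost is one word, one clause and a check of the event coding, with no new assessments and no change to the sample size. If events have already been entered, their nodal dates and any axillary soft-tissue relapses should be reviewed without reference to allocation.

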## 4. STUDY DESIGN

A phase III randomised, multicentre, trial of standard axillary treatment (either ALND or ART) compared with no further axillary treatment after NACT and surgery for early stage breast cancer.

An integrated feasibility study, with embedded qualitative research, will assess the willingness of clinicians and patients to participate in the ATNEC trial.

## 5. ELIGIBILITY CRITERIA

#### 5.1. Inclusion Criteria

Eligible participants will be/should have:

- Age ≥ 18
- Male or female
- T1-3N1M0 breast cancer at diagnosis (prior to NACT)
- FNA or core biopsy confirmed axillary nodal metastases at presentation
- Oestrogen receptor and HER2 status evaluated on primary tumour
- Received standard NACT as per local guidelines (Patients undergoing neoadjuvant endocrine therapy as part of another clinical trial are eligible)

- Ultrasound of the axilla at completion of NACT
- Undergo dual tracer sentinel node biopsy after NACT and at least 3 nodes removed (sentinel nodes and marked node). If axillary node sampling is performed following failed localisation of sentinel nodes, patient will be eligible if at least 3 nodes removed (including the marked node).
- No evidence of nodal metastases post NACT (isolated tumour cells, micro or macro metastasis)

## 5.2. Exclusion Criteria

Participants will be excluded if they have any one of the following:

- Bilateral invasive breast cancer
- Sentinel node biopsy prior to NACT
- Marked node not removed *except* where at least one node removed shows
  - evidence of down-staging with complete pathological response e.g. fibrosis or scarring and at least 3 nodes removed
- Previous axillary surgery on the same body side as the scheduled targeted sampling
- Any previous cancer within last 5 years or concomitant malignancy *except* 
  - o basal or squamous cell carcinoma of the skin
  - o in situ carcinoma of the cervix
  - o in situ or stage 1 melanoma
  - o contra- or ipsilateral in situ breast cancer

#### 6. STUDY PROCEDURES

#### 6.1. Screening and Consent

#### 6.1.1. Participant Identification

The target population are patients with operable, early stage breast cancer with confirmed axillary nodal metastases on initial needle biopsy who receive NACT.

Potential trial participants will be identified at the routine multi-disciplinary meetings, where patients' eligibility will be assessed. The trial will be introduced and discussed with the patient by the treating clinician at the next suitable clinic appointment and will be followed by a further discussion with the research nurse.

#### 6.1.2. Patient Information Leaflet (PIL)

The aim of the PIL is to provide information about the research study to potential ATNEC participants and to prepare the patient for the possibility of being invited to take part in a research study at an early stage in the patient pathway. This is a short leaflet to introduce the study.

#### 6.1.3. Patient Information Sheet (PIS)

A more detailed PIS will be given to those patients deemed eligible for the trial. The trial will use two PIS; one for participants entering the trial pre-operatively (Recruitment Pathway 1 – see Section 6.2.1.1) and one for participants who are deemed eligible following BCS or mastectomy (Recruitment Pathway 2 - see Section 6.2.1.2).

Patients will be encouraged to take the information sheet home and discuss the trial with their family ahead of making an informed decision. Patients will be given sufficient time to consider the information and reach a decision, this may include coming back to the centre for another clinic visit.

#### 6.1.4. Informed Consent

If a patient has read the PIS, and is happy to participate in the trial, they will be consented and registered into the study. The patient must be given the opportunity to ask questions and to be satisfied with the responses, prior to written consent being given.

#### 6.1.4.1 Responsibilities

It is the responsibility of the Principal Investigator (PI) at each site, or trained delegate, to obtain informed consent for each participant, prior to performing any trial related procedure. The PI may delegate responsibility for obtaining informed consent to other appropriate members of the site research team, for example Consultant Radiologists, Radiographers, Clinical Nurse Specialists and Research Nurses, who must be appropriately trained in obtaining informed consent and in Good Clinical Practice (GCP). Delegation of responsibility for obtaining informed consent must be indicated appropriately on the Site Signature and Delegation Log (SSDL). Participant eligibility should be confirmed by the PI or Investigator(s) who are delegated this task on the SSDL. Other members of the Research Team (e.g. Research Nurse) may assist with this process but responsibility remains with the PI.

#### 6.1.4.2 Process for obtaining informed consent

Full consent must be in writing. This may be obtained in-person, during a scheduled clinic consultation, or remotely, through the patient completing the informed consent form (ICF) at home. When completed remotely, the patient should return all sections of the signed form to a named individual at the recruiting site; this can be done using any of the following methods:

- by post
- electronically (e.g. patient sends a scan or photograph of the completed consent form to an approved NHS email address)
- in person (at patient's next clinic visit)

The local PI, or designee receiving consent, must countersign the consent form. There is no requirement that the counter signature date matches the date of the participant signature where this has been completed remotely, but the counter signatory must be satisfied that the consent is genuine. Where the participant has returned an image of the signed form, this should be printed. If the printed image is unsuitable for countersignature, the investigator should sign a blank consent form and attach the printed image.

A patient cannot be randomised to the trial until evidence of written informed consent has been received by the recruiting site.

